5.3. PATIENT EXCLUSION CRITERIA

A patient who meets *any of the following criteria will not be included* in the study:

- (a) Life expectancy <2 years as judged by the investigator;
- (b) Psychiatric or other condition that may interfere with the study;
- (c) Participating in the enrollment or 30-day follow-up phase of another clinical study;
- (d) Known allergy to any device component;
- (e) Coagulopathy or uncontrolled bleeding disorder;
- (f) Contraindication to contrast media or anticoagulants;
- (g) Ruptured, leaking, or mycotic aneurysm;
- (h) Aortic dissection;
- (i) Serum creatinine (S-Cr) level >2.0 mg/dL;
- (j) Traumatic vascular injury;
- (k) Active systemic or localized groin infection;
- (l) Connective tissue disease (e.g., Marfan's Syndrome);
- (m) Recent (within prior three months) cerebrovascular accident or myocardial infarction;
- (n) Prior renal transplant;
- (o) Length of either renal artery to be stented <13mm;
- (p) Significant occlusive disease of either renal artery (>70% stenosis);
- (q) An essential accessory renal artery (supplies more than 25% of the renal parenchyma);[‡]
- (r) Indispensable inferior mesenteric artery;
- (s) Aneurysmal disease of the descending thoracic aorta;
- (t) Clinically significant mural thrombus in the suprarenal segment;[¥]
- (u) Prior iliac artery stent implanted that may interfere with delivery system introduction;
- (v) Unsuitable vascular anatomy;
- (w) Pregnancy (female patient of childbearing potential only);
- (x) Existing renal stent;
- (y) Pre-planned need for concomitant procedure (e.g. surgical conduit for vascular access, hypogastric artery embolization/coil, renal artery angioplasty)

[‡]Patients who undergo prior embolization of an essential accessory renal artery may be considered for trial enrollment.

[¥]Mural thrombus >5mm in thickness over >60% of the aortic circumference.

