6. RESPONSE MEASURES

6.1. SAFETY

The safety endpoint is defined as the incidence of Major Adverse Events (MAE), defined as the composite of the following as determined by the independent Clinical Events Committee (CEC). Event definitions are provided in §8.7.7.

- *All-Cause Mortality;*
- *Bowel Ischemia;*
- *Myocardial Infarction;*
- *Paraplegia;*
- *Renal Failure;*
- *Respiratory Failure;*
- *Stroke;*
- *Blood Loss >1,000cc*

Refer to §10.6 for primary safety endpoint analysis details.

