8.4. SCHEDULE OF MEASUREMENTS

A summary of the tests and measurements to be conducted pre-study/at baseline, operatively, prior to discharge, and during follow-up is illustrated in the following chart.

Schedule of Tests:	Screening/ Baseline	Procedure (Day 0)	Pre- Discharge	1 Month*	6 Months*	1 to 5 Years*
Physical Exam [†]	x		x	x	x	x
Blood Labs [‡]	x		x	x	x	x
Contrast-Enhanced CT Scan [¥]	x			x	x	x
Ankle Brachial Index	x		x	x	x	x
Adverse Events		x	x	x	x	x

[†]The physical exam includes overall health and physical assessment and vital signs.

[figure not shown]
[‡]Blood labs include serum creatinine, blood urea nitrogen, hematocrit, and hemoglobin.

[¥]The baseline high resolution, contrast-enhanced CT scan (2mm or less slice spacing) performed within three months prior to enrollment will be reviewed by the independent core lab for patient eligibility determination. Evaluations of endograft performance, renal stent graft patency and integrity, and stent graft patency and integrity will be made based upon post-operative CT scan evaluations by the core laboratory.

*Follow-up windows are ±2 weeks (1 month visit); ±1 month (6 month visit); ±2 months (Year 1 visit); ±3 months (Years 2 through 5 visits)

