8.7.7. Clinical Events Committee Review

Overview

The clinical events committee (CEC) identified in §2 consists of at least three physicians who will serve as independent experts responsible for evaluation and categorization of adverse events reported by the investigators in the trial. Analyses of events described in this protocol will be based on the CEC-determined categorization.

The primary purpose of these individuals is to ensure a consistent, independent review of events and their clinical significance using standardized criteria and definitions. A curriculum vita for each CEC member is maintained by Endologix, and is available for regulatory review. Due to the need for independence, these individuals may not participate in this trial as investigators, and may not hold significant material, financial or other interests which create a potential conflict with respect to this role, including but not limited to significant equity

interest in Endologix.

Process

Endologix will provide independently to the CEC the complete case report form event text that details all deaths and the events as reported by the clinical site investigators. This information will be provided without identification of the site name, and will identify patients by identification number and initials only. Non-serious events or events that are reported as clearly unrelated events will not be assessed by the CEC. The CEC will review events and any follow-up data requested from Endologix. This may include copies of such documents as progress notes, operative notes, discharge summaries, death summaries, and autopsy reports.

The CEC will document the event categorization for each event individually. Meeting notes and supporting information, requests for documentation, etc. will be maintained.

Event Definitions

The following event definitions will be applied to the Primary Endpoint Analysis during this study. Where possible, events will be categorized as being related to the endovascular procedure/bifurcated device, to the fenestrated device, or to the renal stent graft device.

- *Death*: Any death occurring during the study period, regardless of cause.

Death will be further subcategorized as early (within 30 calendar days from the date of the procedure) or late (>30 days). It will also be subcategorized as aneurysm-related or not aneurysm-related.

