Aneurysm-related death is defined as: any death occurring within 30 days from the date of the procedure, regardless of cause, and death due to aneurysm rupture or following any procedure intended to treat the aneurysm.

- *Procedural Technical Failure*: An event occurring procedurally or within 30 days post-procedurally that meets one or more of the following criteria:
 - *Aortic Stent Graft Failure* is defined as a failure of the bifurcated or fenestrated proximal extension stent graft to be delivered and deployed, such that the procedure is not completed, or the device failure results in a serious complication, or a residual Type I or III endoleak that cannot be resolved during the index procedure;
 - *Renal Stent Graft Failure* is defined as a failure of the renal stent graft to be delivered and deployed, such that the procedure is not completed, or the device failure results in a serious complication.
- *Major Adverse Event*: An event occurring during the trial that meets one of the following criteria:
 - *All-Cause Death* (see above).
 - *Bowel Ischemia*: the lack of adequate blood flow to the intestines that requires

intensification of medical therapy or surgical/endovascular intervention.

- *Myocardial Infarction*: the presence of raised levels of one or more cardiac biomarkers in comparison to laboratory reference ranges;
 - *Paraplegia*: Paralysis of the lower extremities inclusive of the lower trunk.
 - *Renal Failure*: the need for temporary or permanent dialysis or >0.5mg/dL increase in pre-operative serum creatinine level at two consecutive intervals;
 - *Respiratory Failure*: pneumonia or respiratory failure requiring ventilator support beyond 24 hours post-procedure;
 - *Stroke*: a sudden development of neurological deficit due to vascular lesions of the brain such as hemorrhage, embolism, or thrombosis that persists for >24 hours.
 - *Blood Loss >1,000cc*: Estimated blood loss during the index procedure $\geq 1,000$ cc.
- *Other Definitions*:
- *Aneurysm Enlargement*: Core Lab reported aneurysm sac diameter increase of >5mm in late follow-up as compared to the initial post-operative measurement.
 - *Aneurysm Rupture*: internal bleeding or leaking of blood from the aneurysm subsequent to the index procedure.

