 - *Conversion to Open Repair*: open surgical repair of the abdominal aortic aneurysm due to unsuccessful delivery or deployment of the stent graft, due to complications or other clinical situations that precluded successful endovascular treatment, or at any time following initial successful endovascular treatment for any reason.
 - *Cardiac Morbidity*: acute myocardial infarction (diagnosed based on measured levels of one or more cardiac biomarkers in comparison to laboratory reference ranges); new onset heart failure (an acute episode or exacerbation of existing low cardiac output accompanied by distal and/or pulmonary edema); intractable or malignant arrhythmia requiring cardioversion or pacemaker placement; or coronary intervention (coronary artery bypass grafting [CABG] or percutaneous coronary intervention [PCI]).
 - *Clinically Significant Device Migration*: Core Lab reported aortic stent graft movement >10mm from the original implant location resulting in an intervention or in a serious complication.
 - *Renal Dysfunction*: a reduction in the estimated glomerular filtration rate (eGFR) of >30% from the preoperative value;
 - *Secondary Procedure*: any non-diagnostic intervention after the index procedure intended to correct or repair an endoleak, limb occlusion, migration, aneurysm sac expansion and/or a device defect;
 - *Stent Graft Occlusion*: Intervention for aortic or renal stent graft occlusion or as reported by the Core Laboratory.

- *Transient Ischemic Attack*: a sudden development of neurological deficit due to vascular lesions of *the* brain such as hemorrhage, embolism, or thrombosis that persists for <24 hours.
- *Type I/III/IV Endoleak*: Core Lab reported endoleak: between the endograft and the vessel either at the proximal attachment point (Type IA) or at the distal attachment point (Type IB); between endograft components (Type III); or transgraft (Type IV)
- *Type II Endoleak*: Core Lab reported endoleak emanating from a patent collateral vessel (e.g., inferior mesenteric artery; lumbar artery; etc.).

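### The biomarker-only definition of myocardial infarction can count a stable elevation as an infarction and miss one shown only by ECG or imaging, which weakens the separately reported MI component and late MAEs but not the primary safety conclusion

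*Combined protocol and SAP*

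**What the plan says.** MI is one of eight components of the primary safety composite (section 6.1). Section 8.7.7 defines it as "the presence of raised levels of one or more cardiac biomarkers in comparison to laboratory reference ranges". Of its definitions the section says: "The following event definitions will be applied to the Primary Endpoint Analysis during this study". Section 11.1(f) also has the Clinical Events Committee (CEC) categorise events by the protocol's definitions. The Cardiac Morbidity entry in 8.7.7 adds the word acute, but its test is again a biomarker against the laboratory range. No other section adds an MI criterion.

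On data collection, section 8.4 states: "Blood labs include serum creatinine, blood urea nitrogen, hematocrit, and hemoglobin". Sections 8.6.3, 8.6.6 and 8.6.7 list the same four tests at baseline, before discharge and at follow-up. The schedule contains no cardiac biomarker and no ECG. Section 5.3 excludes patients with "Recent (within prior three months) cerebrovascular accident or myocardial infarction", so an older infarction does not bar entry. Heart failure is not listed as an exclusion, and section 10.6.3 includes both heart failure and prior MI among its covariates.

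On adjudication, section 8.7.7 says: "Non-serious events or events that are reported as clearly unrelated events will not be assessed by the CEC".

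MI is also reported on its own: with an exact 95% confidence interval at 30 days (10.6.4), and by component within and after 30 days (10.8.4). It enters the late MAE composite as well (10.8.5).

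**The concern.** The rule is a single threshold at the laboratory limit. It does not ask whether the value is new for that patient, or whether anything clinical accompanied it. Another component in the same list is tied to the patient's own baseline: renal failure can be met by ">0.5mg/dL increase in pre-operative serum creatinine level at two consecutive intervals". MI has no such anchor, and because no baseline biomarker is scheduled, a chronic elevation often could not be told from a new one.

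Two errors follow from the wording. A patient whose marker sits above range before and after the procedure meets the definition. A patient with a non-fatal infarction shown by ECG or imaging, in whom no biomarker was drawn, does not. Since testing is left to the sites, the recorded MI rate partly reflects how often they order the test.

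At stake is whether the MI rate, and the late MAE rates that contain it, measure what their names say. The late rates run to five years and have no large planned difference from a control group to absorb misclassification.

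**Working it through.** **Step 1. What the wording counts.**

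| Case | Present rule | Why |
|---|---|---|
| Stable marker above range, before and after | MI, if it reaches the CEC | no comparison with own value |
| Isolated marker above range, no cardiac finding | MI, if it reaches the CEC | no clinical criterion |
| Non-fatal infarction on ECG or imaging, no biomarker drawn | not MI | biomarker is the only route |
| Fatal infarction, no biomarker | MAE as death, not MI | all-cause death is a component |

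**Step 2. The plan's own figures.** Section 10.6.2 gives 81% power for 97 test against 66 control patients at MAE rates of 0.434 and 0.670, one-sided alpha 0.025. Enumerating the one-sided Fisher exact test gives 80.99%, so the figure reproduces. The same section's table gives MI as 3/192 (1.6%, printed as 1.5%) in the earlier endovascular group and 5/66 (7.6%) in the surgical controls. Composite MAE in the controls is 44/66 (66.7%), driven by blood loss at 38/66.

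**Step 3. Scale of the MI component.** At the earlier endovascular rate, 97 × 3/192 = 1.5 MIs are expected. One misclassified patient moves the MI rate by 1/97 = 1.03 percentage points. Two extra would take 1.5 to 3.5, or 2.3 times. This shows how sensitive a small count is. It does not forecast how many patients would be misclassified.

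**Step 4. Can the primary safety conclusion change?** The planned test rate gives 97 × 0.166 = 16 MAEs. The largest test-group counts that still reject at one-sided 0.025 are below. The control comparisons are unadjusted Fisher tests, not the propensity-stratified test of 10.6.4. The last row is the exact binomial fallback.

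| Comparison | Rejects up to | Extra MAEs beyond 16 needed to fail |
|---|---|---|
| Controls as recorded, 44/66 | 48/97 (49.5%) | 49 − 16 = 33 |
| All 5 control MIs false and each the patient's only MAE, 39/66 (59.1%) | 40/97 (41.2%) | 41 − 16 = 25 |
| Fallback goal of 56% | 44/97 (45.4%) | 45 − 16 = 29 |

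Take a deliberately extreme assumption: 20% of the 97 (19 patients) are scored as MI with no other MAE. That gives 16 + 19 = 35 MAEs (36.1%). One-sided P is 0.0001 against 44/66, 0.003 against 39/66 and 0.00006 against 56%. All pass.

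The same limits cover under-counting. At least 25 to 33 test patients would need an unrecorded non-fatal infarction, and no other MAE, before the result failed.

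**The case against.** The strongest reply is that the over-counting cases seldom get through the reporting path. The CEC reviews only investigator-reported events that are serious and not clearly unrelated. Under section 8.7.1, serious means death, threat to life, new or prolonged hospitalisation, disability or birth defect. A slightly raised marker with no clinical consequence would normally stop there, and many patients would never be tested. The CEC is also there to review clinical significance and may request further records. Missed infarctions need a documented non-fatal event in which no biomarker was ever drawn, which is narrow.

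Most of this stands, and it limits the size of the problem. It does not repair the rule. A patient hospitalised for another reason with a chronically raised marker can pass the filter, and the CEC is then bound to the written definition. The filter also does nothing for infarctions with no biomarker.

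A reader might infer that the MI rate will be several times too high, for example by assuming that 5% to 20% of the 97 patients (5 to 19) are falsely scored. The documents do not support this. They give no rate of testing or of chronic elevation, and the filter makes the upper end unlikely. Nor do they say how MI was defined or ascertained in the 2000–2003 controls, so no direction of bias between test and control can be claimed.

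**Conclusion.** The defect is real and lies in the stated rule: it can score a stable elevation as an infarction and leave out a non-fatal infarction that has other documentation. It affects the validity of the separately reported MI component and of late MAEs. Its size cannot be quantified from the documents.

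It would be wrong to conclude that the primary safety result is in doubt. At the planned rates the test would survive even the extreme case of 35/97. That finding rests on the planned 16.6% MAE rate, 97 test patients, and unadjusted tests standing in for the stratified one. Sample size and power are unaffected. The change is worth making because it is cheap and the MI count is small enough for a few patients to alter it.

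**What to change.** In section 8.7.7, have the CEC classify every adjudicated cardiac event two ways:

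- **(a)** the present biomarker-only rule;
- **(b)** infarction only if the elevation is new against an earlier or serial value and is supported by symptoms, ECG or imaging, or if ECG, imaging or autopsy documents an infarction without a biomarker.

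Report the MI component and late MAEs under (b), with (a) alongside.

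For the primary comparison with controls, use (b) only if all control cardiac records can be classified the same way. Re-reviewing only the five recorded control MIs could remove control events but never add any. If the full set cannot be classified, keep (a) in both arms and show (b) as a sensitivity analysis. Do the same for the fallback test, because the published outcomes behind the 56% goal cannot be reclassified. Never mix rules between arms.

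The cost is definition wording and some CEC re-review. Section 10.6.2 says patient-level control data exist, but some control records may lack serial values or ECGs. The change does not remove the dependence on site testing, since cardiac biomarkers remain unscheduled; the report should say so.

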6.2. EFFECTIVENESS

The primary effectiveness endpoint is defined as the rate of Treatment Success at one year. Treatment Success is a composite of outcomes clinically relevant to the endovascular repair of JAA/PAA as follows. Event and related definitions are provided in §8.7.7.

- Procedural Technical Success;
- Absence of:
 - Aneurysm rupture;
 - Conversion to open repair;
 - Type I endoleak >30 days;
 - Type III endoleak;
 - Clinically significant migration;
 - Aneurysm enlargement;
 - Secondary intervention for resolution of endoleak, limb occlusion, migration, aneurysm sac expansion and/or a device defect

Refer to §10.7 for primary effectiveness endpoint analysis details.

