8.7.4. Anticipated Adverse Events

Adverse events that could potentially occur during this investigation are called anticipated adverse events and are listed in alphabetical order:

- Access site complications and sequelae (e.g., dehiscence, infection, pain, hematoma, pseudoaneurysm)
- Allergic reaction to contrast agent (e.g., pruritus, urticaria, bronchospasm, angioedema, hypotension or anaphylaxis that occurs during or post-procedure)
- Amputation
- Anesthetic complications and sequelae (e.g., aspiration)
- Aneurysm enlargement
- Aneurysm rupture
- Arterial damage or trauma (e.g., bleeding, perforation, dissection, rupture)
- Arterial or venous thrombosis and/or pseudoaneurysm
- Arteriovenous fistula
- Bleeding requiring transfusion and/or surgical intervention
- Bowel complications (e.g., ileus, ischemia, infarction, necrosis)
- Cardiac complications and sequelae (e.g., arrhythmia, myocardial infarction, congestive heart failure, hypotension, hypertension)
- Catheter fragmentation and sequelae (e.g., embolization, vessel trauma)
- Claudication
- Coagulopathy
- Death (due to any cause)
- Edema
- Embolization (micro and macro) with transient or permanent ischemia or infarction
- Endoleak
- Fever and localized inflammation
- Genitourinary complications and sequelae (e.g., ischemia, fistula, incontinence, hematuria, impotence, infection)
- Hepatic failure
- Infection of the aneurysm, device access site, including abscess formation, transient fever and pain.
- Local or systemic neurologic complications and sequelae, transient or permanent (e.g., stroke, transient ischemic attack, paraplegia, paraparesis, paralysis, numbness and/or tingling in legs)
- Lymphatic complications and sequelae (e.g., lymph fistula)
- Thrombosis or occlusion of stent graft or arterial vessel of the lower extremities
- Pulmonary/respiratory complications and sequelae (e.g., pneumonia, respiratory failure, prolonged intubation, pulmonary embolism)
- Renal complications and sequelae (e.g., artery occlusion, infarction, insufficiency, failure)
- Secondary procedure
- Stent graft: improper component placement; incomplete component deployment; component migration; suture break; occlusion/thrombosis; infection; stent fracture; graft material wear; dilatation; erosion; puncture and perigraft flow
- Surgical conversion to open repair

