10.7.2 Sample Size

The primary trial effectiveness variable is the Treatment Success rate at one year post-operatively. Treatment Success is a composite of clinically-relevant outcomes, including procedural technical success and absence of: aneurysm rupture, conversion to open repair, Type I endoleak after 30 days; Type III endoleak; clinically significant migration; aneurysm enlargement; or secondary intervention for resolution of endoleak, limb occlusion, migration, aneurysm sac expansion and/or a device defect.

The sample size is obtained by using the exact binomial distribution using PASS 2008. A sample size of 82 patients at one year in the test group will have 80.58% power against a null performance goal of 80% if the proportion of Treatment Success is 90% or higher for alpha = a one-sided 0.05. It is estimated that the rate of Treatment Success will be greater than 90%.

It is anticipated that the drop-out rate of the trial will be 15% or less. Because the larger of the two sample sizes after adjustment for loss to withdrawal is the one for effectiveness, $82/0.85 = 97$ patients will need to be recruited for this trial.

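### Type III endoleak covers only leaks between components, so a leak through a defect in the graft wall does not by itself fail Treatment Success

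*Combined protocol and SAP*

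**What the plan says.** Section 8.7.7 states that "The following event definitions will be applied to the Primary Endpoint Analysis during this study", so its wording governs the primary effectiveness result. Endoleaks other than Type II are classed there, on Core Lab report, as Type I (between endograft and vessel) or as "between endograft components (Type III); or transgraft (Type IV". Type IV is not divided into flow through intact material and flow through a defect.

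On endoleak, Treatment Success names two types as failures in their own right. Section 6.2 lists "Type I endoleak >30 days" and Type III without a time limit, and 10.7.2 repeats the list: "Type I endoleak after 30 days; Type III endoleak; clinically significant migration; aneurysm enlargement". Under Procedural Technical Failure, the endoleak clause is "a residual Type I or III endoleak that cannot be resolved during the index procedure". Type IV appears in none of these.

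One component of the composite does not depend on leak type, but it requires treatment: "Secondary intervention for resolution of endoleak, limb occlusion, migration, aneurysm sac expansion and/or a device defect".

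Among the anticipated adverse events in 8.7.4 are suture break and "graft material wear; dilatation; erosion; puncture and perigraft flow". Endoleak of any type and graft integrity are reported descriptively in 10.8.11 and 10.8.14.

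**The concern.** An untreated Type III leak fails the patient with no sac growth and no complication. An untreated leak through a tear in the graft wall also lets flow past the graft, yet on the literal wording it is Type IV and does not count by itself. The documents give no reason for treating the two differently.

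The protocol anticipates loss of graft integrity in 8.7.4, and the investigational component has an oversized, unsupported ePTFE midsection (7.1). At stake is whether the primary effectiveness endpoint registers that kind of failure directly or only through a later consequence. Any effect on the reported rate runs towards success.

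**Working it through.** **1. How a graft-wall leak is scored.** Take a leak through a hole, tear or suture-line defect, away from any junction between components.

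| Rule | Counts the leak? |
|---|---|
| Type I after 30 days (6.2, 10.7.2) | No: not between endograft and vessel |
| Type III (6.2, 10.7.2) | No: not between components |
| Residual leak in Procedural Technical Failure (8.7.7) | No: Types I and III only |
| Device failure in Procedural Technical Failure (8.7.7) | Only procedurally or within 30 days, and only with a serious complication or a procedure not completed |
| Secondary intervention (6.2) | Only if treated |
| Conversion (8.7.7) | Only if converted, for whatever reason |
| Aneurysm rupture (8.7.7) | Only if it ruptures |
| Aneurysm enlargement (8.7.7) | Only if sac growth exceeds 5 mm |
| Endoleak and graft-integrity tables (10.8.11, 10.8.14) | Recorded, outside the primary endpoint |

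A patient with such a leak and none of these consequences by one year is a success, provided the rest of the composite is met.

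**2. The plan's own figures (10.7.2).** Inputs: n = 82, performance goal 80%, assumed success 90%, one-sided alpha 0.05, dropout 15%. The pass mark r is the smallest count with P(X ≥ r | n, 0.80) ≤ 0.05, where X is binomial.

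- n = 82: r = 72, so at most 82 − 72 = 10 failures. P(X ≥ 72 | 0.80) = 0.0458, and P(X ≥ 71 | 0.80) = 0.0836.
- Power: P(X ≥ 72 | 0.90) = 0.8057, against 80.58% stated.
- Enrolment: 82/0.85 = 96.5, rounded up to 97.

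These reproduce. At the boundary, one patient moved from success to failure reverses the result.

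**3. Illustration of size.** Let m be the proportion of patients whose only failure would be an uncounted graft-wall leak. The documents give no value, so m = 1% to 4% is an assumption. At n = 82 that is 0.8 to 3.3 patients (82 × 0.01 to 82 × 0.04). If success is 80% with these leaks counted as failures, the rate as scored is 0.80 + m, and the chance of passing is P(X ≥ r | n, 0.80 + m).

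| m | n = 82, pass at 72 or more | n = 97, pass at 85 or more |
|---|---|---|
| 0 | 4.6% | 3.5% |
| 1% | 7.1% | 5.7% |
| 2% | 10.7% | 9.1% |
| 3% | 15.5% | 13.9% |
| 4% | 21.9% | 20.4% |

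The n = 97 column is there because the primary analysis is ITT with imputation (10.1, 10.2). It treats all 97 as having an outcome and ignores imputation variance.

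**The case against.** A reader might infer that any untreated leak through the graft is automatically a success. The documents do not support that: the consequences in the table above each fail the patient, and a leak that is treated already counts.

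A reader might also infer that leaks at the fenestrations, the most device-specific site, are lost. That does not follow either. The fenestrations receive renal stent grafts (7.1), and a leak between a renal stent graft and its fenestration can be read as lying between two endograft components, hence Type III and a failure. The gap is in the graft wall away from such junctions.

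A third tempting reading is that type I error is inflated. Under Treatment Success as the protocol defines it, the exact test keeps its size. The table shows how the result depends on which endpoint is meant. The documents do not derive the 80% goal, so it is unknown whether fabric leaks were counted in setting it.

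Several further objections have weight. Section 8.7.4 is a general list without rates, and nothing says the loose midsection is prone to tearing. The leaks stay visible in the descriptive tables, with a determination of association with an SAE or device malfunction. Classification belongs to the Core Lab, whose reading instructions are not in the documents, and it might in practice call a tear Type III. These points limit the likely size. They do not remove the gap: a Core Lab that read tears as Type III would depart from 8.7.7, and a primary-endpoint call would rest on an unwritten convention.

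**Conclusion.** The point stands in a limited form. As written, a leak through a defect in the graft wall, away from a component junction, does not by itself fail Treatment Success, whereas an untreated Type III leak does. This follows from the stated definitions rather than from missing detail.

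Its size is unknown. The illustrative rise in the chance of passing, from 4.6% to between 7.1% and 21.9% at n = 82 (3.5% to between 5.7% and 20.4% at n = 97), rests on two assumptions: that 1% to 4% of patients have only such a leak with no other failing event, and that success is exactly 80% when those leaks count as failures. The sample-size figures themselves are correct. This is a cheap improvement to one definition and does not invalidate the primary test.

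**What to change.** In 8.7.7, define Type III as a leak between endograft components, including between a renal stent graft and its fenestration, or through a hole, tear or suture-line defect in the graft material. Limit Type IV to flow through intact graft. Give the Core Lab the same wording. The existing Type III terms in 6.2, 10.7.2 and Procedural Technical Failure then pick up these leaks without further edits.

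If the sponsor keeps the current definition, prespecify a sensitivity analysis of Treatment Success that counts fabric-defect leaks as failures.

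The cost is one definition and one reading instruction. CT scans and Core Lab readings are already scheduled, so no imaging, visits or patients are added. The reported success rate may be slightly lower. If the planned 90% counted such leaks as successes, power at n = 82, P(X ≥ 72 | 0.90 − m), would fall from 80.6% to 71.1% at m = 1% and 60.4% at m = 2%, so the sponsor should state what the 90% assumed.
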